#### 5.4.3.1.1 Clinical Laboratory Tests

A urine pregnancy test is to be performed every 3 months (pediatric subjects) or every 6 months (adult subjects) after starting ETR (females of childbearing potential only).

After termination of data collection (see Figure 1), clinical laboratory tests will occur according to the local standard of care and documented in the subject's medical records only.

## 5.5 Safety Management Guidelines for Cutaneous Events

Toxicity management is at the discretion of the investigator, and is to take into account the protocol-defined procedures defined under 5.5.1 and 5.5.2, and the local standard clinical practice.

After termination of data collection (see Figure 1), toxicity management will be performed per local standard of care and documented in the subject's medical records only.

Clinical data in adults have shown that ETR is generally safe and well tolerated. As rash is a known class effect with NNRTIs, cutaneous events as described below have been closely monitored in trials with ETR. Rash events with ETR are now well characterized based on the large safety dataset from our double-blind placebo-controlled trials. This section describes the guidelines for management of rash and acute allergic reactions.

In general, all other AEs that are ongoing at the end of the treatment period should be followed up until satisfactory clinical resolution or stabilization at the investigator's discretion as per the local standard clinical practice.

### 5.5.1 RASH MANAGEMENT

#### **Rash**

In case of rash, visits and assessments should be performed as described below and in the "Visit Schedule for Rash Management in Pediatric Patients" (see Section 7.4, Attachment 4) and "Visit Schedule for Rash Management in Adult Patients" (see Section 7.5, Attachment 5). Unscheduled follow-up visits for close follow-up of rash will be performed based on the grade (severity) of the rash. At the investigator's discretion, additional visits and assessments can be performed.

Dermatologist fees for evaluating subjects who experience a rash will be reimbursed by the sponsor.

The following grades are based on the DAIDS grading table (see Section 7.2, Attachment 2), with adaptations made by the sponsor.

**Subjects (and/or their legally acceptable representative) should be informed that they should contact their doctor and visit the clinic immediately when they notice any rash.**

#### **Grade 1 and 2 Cutaneous Reaction/Rash**

A grade 1 cutaneous reaction/rash is defined as localized macular rash.

A grade 2 cutaneous reaction/rash is defined as diffuse macular, maculopapular, or morbilliform rash or target lesions.

Subjects experiencing a grade 1 or 2 rash or cutaneous event may continue treatment or have their trial medication interrupted at the investigator's discretion. Local safety sampling at the time of the rash and clinical follow-up for these AEs will be at the discretion of the investigator, however, close clinical follow-up is recommended to monitor for any progression of the AE.

#### **Grade 3 or 4 Cutaneous Reaction/Rash**

A grade 3 cutaneous reaction/rash is defined as:

- Diffuse macular, maculo-papular, or morbilliform rash with vesicles or limited number of bullae
- Superficial ulceration of mucous membrane limited to 1 site
- Cutaneous reaction/rash with at least 1 of the following\*:
  1. elevations of ALT/AST > 2 x baseline but at least 5 x ULN\*
  2. fever  $\geq 38^{\circ}\text{C}$  or 100 F\*
  3. serum sickness-like reaction\*
  4. eosinophil count > 1000/mm^3\*

*\* added by the sponsor.*

A grade 4 cutaneous reaction/rash is defined as:

- Extensive or generalized bullous lesions
- Stevens-Johnson syndrome (SJS)
- Ulceration of mucous membrane involving 2 or more distinct mucosal sites
- Toxic epidermal necrolysis (TEN).

Subjects experiencing a grade 3 or 4 rash or cutaneous event must have their trial medication discontinued and be withdrawn from the trial. Referral to a dermatologist is recommended for these events. Local safety sampling to determine possible liver or systemic abnormalities is recommended. Close clinical follow-up and appropriate medical intervention is recommended for these events; daily follow-up is recommended for 5 days from the onset of the event to monitor for progression of the event.

### 5.5.2 ACUTE SYSTEMIC ALLERGIC REACTION

#### **Grade 1 (localized urticaria [wheals] with no medication intervention indicated):**

Subjects may continue the investigational medication for a grade 1 acute systemic allergic reaction. The subject should be advised to contact the investigator immediately if there is any worsening of the localized urticaria, if any systemic signs or symptoms develop. Antihistamines or topical corticosteroids or antipruritic agents may be prescribed as long as these are in line with the package inserts of the ARVs or the (dis)allowed medications for ETR as indicated above.

#### **Grade 2 (localized urticaria with medical intervention indicated, or mild angioedema with no medical intervention indicated):**

Subjects may continue the investigational medication for a grade 2 acute systemic allergic reaction. If there is any worsening of the acute systemic allergic reaction, the subject should be advised to contact the investigator immediately and to discontinue the investigational medication and be withdrawn from the trial. Antihistamines or topical corticosteroids or antipruritic agents may be prescribed as supportive care as long as these are in line with the package inserts of the ARVs or the (dis)allowed medications for ETR as indicated above.

#### **Grade 3 (generalized urticaria, or angioedema with medical intervention indicated, or symptomatic mild bronchospasm) and grade 4 (acute anaphylaxis, or life-threatening bronchospasm, or laryngeal edema):**

Subjects will permanently discontinue trial medication and be withdrawn from the trial. Rechallenge with ETR is not allowed. Subjects will be treated as clinically appropriate. Standard management should be undertaken.

## 5.6 Toxicity Management for Specific Adverse Events With Concomitant Antiretrovirals

Toxicity management is at the discretion of the investigator, and is to take into account the protocol-defined procedures defined under 5.6.1, 5.6.2, 5.6.3, 5.6.4, 5.6.5, and 5.6.6, and the local standard clinical practice.

After termination of data collection (see Figure 1), toxicity management will be performed per local standard of care and documented in the subject's medical records only.

*(The information below does not imply that the following AEs are caused by concomitant ARVs alone, but may also be due to ETR.)*

### 5.6.1 HYPERGLYCEMIA

#### **Grade 3: 13.89-27.75 mmol/L (251-500 mg/dL)**

#### **Grade 4: > 27.75 mmol/L (> 500 mg/dL)**

If elevated glucose levels are from a non-fasting blood draw, repeat the draw after a 10-hour fast. Management decisions must be based on fasted results. Subjects who experience asymptomatic glucose elevations of grade 3 or 4 and subjects with pre-existing diabetes may continue trial medication unless clinical assessment foresees an immediate health risk to the subject. Subjects with persistent grade 3 or 4 glucose elevations despite appropriate anti-hyperglycemic treatment

should be permanently discontinued with the exception of subjects with pre-existing diabetes. Appropriate clinical management of hyperglycemia must be started in a timely fashion.

### **5.6.2 HYPERTRIGLYCERIDEMIA AND HYPERCHOLESTEROLEMIA**

**Hypertriglyceridemia            Grade 3: 8.49-13.56 mmol/L (751-1200 mg/dL)**

**Grade 4: > 13.56 mmol/L (> 1200 mg/dL)**

**Hypercholesterolemia        Grade 3: > 7.77 mmol/L (> 300 mg/dL)**

**Grade 4: not applicable**

Management decisions should be based on fasted results. If elevated triglyceride or cholesterol levels are from a non-fasting blood draw, repeat the draw after a 10-hour fast. Subjects who experienced asymptomatic triglyceride elevations of grade 3 or 4 or cholesterol elevations of grade 3 may continue to receive trial medication.

Hypertriglyceridemia and hypercholesterolemia should be treated according to the specific guidelines for treating HIV-infected subjects. Appropriate clinical management of dyslipidemia in the setting of HIV disease should be started in a timely fashion. Investigators may choose to initiate pharmacologic treatment in addition to the usual counseling on diet and exercise. Medications should be introduced with caution. Lovastatin and simvastatin are not allowed as there is the potential for a significant drug interaction with PIs (ATV/rtv).

### **5.6.3 LACTIC ACIDOSIS**

The relevance of asymptomatic lactic acid elevations is unclear, and lactates are not part of the routine safety evaluations for this trial. Routine lactate monitoring is not currently recommended. However, lactate monitoring should be performed if there is a clinical suspicion of lactic acidosis (see description below).

A sometimes-fatal syndrome of lactic acidosis, often associated with evidence of hepatic steatosis, is a recognized but rare complication of N(t)RTI therapy. This syndrome is felt to be secondary to mitochondrial toxicity induced by the inhibitory effect of N(t)RTIs on DNA polymerase gamma, a key enzyme needed for mitochondrial DNA synthesis. Current knowledge regarding this syndrome is incomplete. Obesity and prolonged N(t)RTI exposure may be risk factors. Women are also at greater risk. Symptoms of lactic acidosis are frequently non-specific such as fatigue, weakness, and fever, but in the majority of cases also include symptoms suggestive of hepatic dysfunction such as nausea, vomiting, abdominal or epigastric discomfort, abdominal distension, hepatomegaly, and new onset elevated liver enzymes. A high index of suspicion may be required to diagnose this condition. Alternatively, it is possible that unwarranted concern may be raised by over interpretation of lactic acid levels. N(t)RTI toxicity is only one cause of lactic acidosis. Type "B" lactic acid elevations or those without clinically apparent tissue hypoxia are also seen in the context of diabetes mellitus, uremia, liver disease, infections, malignancies, alkaloses, and drug and toxin ingestion of such substances as ethanol, methanol, ethylene glycol, and salicylates.

The following case definition of lactic acidosis, defined differently for symptomatic vs asymptomatic individuals, will be used in this protocol:

### Symptomatic Hyperlactatemia

New, otherwise unexplained and persistent ( $\geq 2$  weeks) occurrence of 1 or more of the following symptoms:

- nausea and vomiting;
- abdominal pain or gastric discomfort;
- abdominal distention;
- increased ALT or AST;
- unexplained fatigue;
- dyspnea;

AND

- lactate level  $> 2$  x ULN confirmed by repeat lactate level analysis.

*Note:* All lactates  $> 2$  x ULN should be repeated as soon as possible, generally within 1 week. Lactate levels should not be assessed following physical exertion as this causes elevated lactate levels and may confound assessment of the clinical significance of these findings. If the second result confirms hyperlactatemia ( $> 2$  x ULN) in subjects with symptoms as described above, subjects should immediately discontinue their current trial regimen (including ETR and other ARVs) and be withdrawn from the trial. Standard management should be initiated with follow-up to resolution.

**Processing of the lactate needs to be done according to strict guidelines both in the preparation of the subject (ideally, fasting and with no recent exercise) and in the blood drawing/processing procedure (ideally, blood drawn without a tourniquet, no hand clenching, blood drawn into a chilled tube and processed immediately) to minimize false elevations of lactates.**

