### **5.2.5 REMOVAL OF SUBJECTS FROM THERAPY OR ASSESSMENT**

Subjects **may** be withdrawn from the trial if:

1. a SAE occurs;
2. they fail to comply with the protocol requirements or to cooperate with the investigator;
3. a grade 3 AE (with the exception of skin events / allergic reaction) occurs according to the DAIDS grading scale. Exceptions (unless clinical assessment foresees an immediate health risk to the subject) are:
  - subjects with pre-existing diabetes who experience a glucose elevation of grade 3;
  - subjects who experience a glucose, triglyceride or cholesterol elevation of grade 3 under non-fasted conditions;
  - subjects who experience asymptomatic glucose, triglyceride or cholesterol elevations of grade 3;
  - subjects who experience asymptomatic pancreatic amylase elevations of grade 3 with no past or active history of pancreatitis;
  - subjects who experience a grade 3 AE that is considered not related or doubtfully related to the study medication;
  - subjects who experience grade 3 absolute neutrophil count or asymptomatic grade 3 platelets.

Subjects **must** be withdrawn from the trial if:

1. the parent(s) or legal representative(s) withdraws consent for a pediatric subject, or the subject withdraws consent or assent;
2. the investigator considers, for safety reasons, it is in the best interest of the subject that he or she is withdrawn;
3. they experience a grade 4 AE or grade 4 laboratory toxicity considered at least possibly related to ETR by the investigator;
4. they experience a grade 3 or higher rash;
5. they experience a grade 3 or higher allergic reaction;

6. they develop clinical hepatitis;
7. pregnancy has been determined.
8. they can be switched to locally available ETR-based treatment regimens (ie, commercially available and reimbursed, or accessible through another source [eg, access program or government program]) or to local standard of care, as appropriate.

The date and the reason for discontinuation must be noted on the Case Report Form (CRF). If consent/assent is not withdrawn, all subjects prematurely discontinuing the trial must be seen for a follow-up visit, if they are not continuing treatment with ETR. The Trial Termination Section of the CRF is to be completed.

**As per Protocol Amendment 3**, study termination will be documented in the subject's medical records and recorded on a separate, paper termination disposition form to be shared with the sponsor.

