#### Laboratory Abnormalities

For asymptomatic grade 1 and 2 pancreatic amylase and/or lipase elevations, and confirmed asymptomatic grade 3 pancreatic amylase elevations with no past or active history of pancreatitis, subjects should be carefully evaluated and followed closely.

For confirmed grade 4 elevations of pancreatic amylase and confirmed grade 3 or 4 elevations of lipase, subjects should interrupt all trial medications until pancreatic amylase and/or lipase returns to grade  $\leq 2$ , at which time trial medication could be reintroduced. N(t)RTIs such as ddI (with or without TDF) and d4T may be resumed at either reduced or full dose at the investigator’s discretion. If grade 4 elevations of pancreatic amylase and/or grade 3 or 4 lipase levels persist  $\geq 14$  days following interruption of all trial medications, or if the toxicity recurs more than twice, all trial medications should be permanently discontinued.

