## **5.7 Statistical Methods Planned and Determination of the Sample Size**

### **5.7.1 SAMPLE SIZE CALCULATION**

No formal sample size calculation has been performed. The trial is not set up to show a specific statistical hypothesis but to provide ETR to subjects who previously received ETR in a clinical (parent) trial sponsored by Janssen Research & Development, and continue to benefit from the use of ETR, in countries where ETR is not commercially available to subjects, is not reimbursed, and is not accessible through another source (e.g. access program or government program), or where the subject is not eligible for ongoing trials/programs with ETR. Data from this trial may be included in Safety Updates.

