| Glucose, serum, high                                  |   |   |   |   |
| Nonfasting  | 116 – 160 mg/dL
6.44 – 8.88 mmol/L   | 161 – 250 mg/dL
8.89 – 13.88 mmol/L  | 251 – 500 mg/dL
13.89 – 27.75 mmol/L | > 500 mg/dL
> 27.75 mmol/L   |
| Fasting   | 110 – 125 mg/dL
6.11 – 6.94 mmol/L   | 126 – 250 mg/dL
6.95 – 13.88 mmol/L  | 251 – 500 mg/dL
13.89 – 27.75 mmol/L | > 500 mg/dL
> 27.75 mmol/L   |

a Revised by the sponsor.

b Values are for term infants.

c Use age- and sex-appropriate values (e.g., bilirubin), including preterm infants.

| LABORATORY                                   |  |  |  |  |
|--|--|--|--|--|
| PARAMETER                                    | GRADE 1
MILD                                    | GRADE 2
MODERATE                            | GRADE 3
SEVERE  | GRADE 4
POTENTIALLY
LIFE-
THREATENING                           |
| Glucose, serum, low                          |  |  |  |  |
| Adult and Pediatric
≥ 1 month     | 55 – 64 mg/dL
3.05 – 3.55 mmol/L         | 40 – 54 mg/dL
2.22 – 3.00 mmol/L     | 30 – 39 mg/dL
1.67 – 2.21 mmol/L                                   | < 30 mg/dL
< 1.67 mmol/L                                    |
| Infanta,b
< 1 month | 50 – 54 mg/dL
2.78 – 3.00 mmol/L         | 40 – 49 mg/dL
2.22 – 2.77 mmol/L     | 30 – 39 mg/dL
1.67 – 2.21 mmol/L                                   | < 30 mg/dL
< 1.67 mmol/L                                    |
| Lactate                                      | < 2.0 x ULN without
acidosis                    | ≥ 2.0 x ULN without
acidosis                | Increased lactate with pH
< 7.3 without life-
threatening consequences | Increased lactate with pH
< 7.3 with life-threatening
consequences |
| LDL cholesterol (fasting)                    |  |  |  |  |
| Adult ≥ 18 years                      | 130 – 159 mg/dL
3.37 – 4.12 mmol/L       | 160 – 190 mg/dL
4.13 – 4.90 mmol/L   | ≥ 191 mg/dL
≥ 4.91 mmol/L  | NA   |
| Pediatric
> 2 – < 18 Years  | 110 – 129 mg/dL
2.85 – 3.34 mmol/L       | 130 – 189 mg/dL
3.35 – 4.90 mmol/L   | ≥ 190 mg/dL
≥ 4.91 mmol/L  | NA   |

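### Section 5.2.5 is not aligned with 5.5.2, 5.6.1, 5.6.3 and 5.6.5 on when etravirine (ETR) is stopped: it exempts some grade 3 events for which those sections direct a stop, and has no specific criterion for two grade 2 situations.

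*Protocol*

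**What the plan says.** Protocol Part I section 5.2.5 has an optional (*may*) list and a mandatory (*must*) list for withdrawal. The optional list includes grade 3 adverse events, with exceptions that apply unless clinical assessment foresees an immediate health risk. Two exceptions matter here: "subjects who experience asymptomatic glucose, triglyceride or cholesterol elevations of grade 3" and "subjects who experience a grade 3 AE that is considered not related or doubtfully related to the study medication". The mandatory list includes allergic reactions from grade 3 upward, grade 4 events at least possibly related to ETR, and a general item for withdrawal on the investigator's safety judgement, which has no grade limit.

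The event sections add their own triggers:

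- **5.6.1, glucose.** "Subjects with persistent grade 3 or 4 glucose elevations despite appropriate anti-hyperglycemic treatment" should be permanently discontinued, except where diabetes pre-existed.
- **5.6.5, lipase.** Confirmed grade 3 or 4 elevations lead to interruption. If they last 14 days or more after interruption, or recur more than twice, "all trial medications should be permanently discontinued". Attribution is not a condition.
- **5.6.3, lactate.** With listed symptoms and a confirmed value above 2 x ULN, "subjects should immediately discontinue their current trial regimen (including ETR and other ARVs) and be withdrawn from the trial". Attribution is again not a condition.
- **5.5.2, allergic reaction.** On any worsening of a grade 2 reaction, the subject should be advised to contact the investigator "and to discontinue the investigational medication and be withdrawn from the trial".

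The grading table in Addendum 2 (section 7.2) puts lactate "≥ 2.0 x ULN without" acidosis at grade 2. Raised lactate with pH below 7.3 is grade 3 without life-threatening consequences and grade 4 with them.

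**The concern.** A site needs one answer on whether ETR stops. Section 5.2.5 is the general removal rule. It repeats some event-section triggers, such as grade 3 or higher rash and allergic reaction, so an investigator could reasonably read it as the summary of the rest. For some events it then points the other way from the event section, or gives no specific criterion.

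The first stake is subject safety and continued access: in the conflicting cases, one section exempts the event from withdrawal and another directs a stop. The second is interpretation. Adverse events leading to discontinuation are one of the four safety summaries in Protocol 5.7.3.1, and they recur in SAP 7.1 and output TSFAE06. Event-related stops also enter the disposition categories in SAP 5.2. If sites relied on different sections, those counts would partly reflect that reliance.

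**Working it through.** No formula applies. The Protocol states in 5.7.1 that "No formal sample size calculation has been performed", no hypothesis is tested, and neither document gives event counts. The check sets each stop instruction below grade 4 against the lists in 5.2.5, using the grades in Addendum 2.

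| Event | Event section | Section 5.2.5 | Result |
|---|---|---|---|
| Asymptomatic grade 3 glucose, persistent despite treatment, no pre-existing diabetes | 5.6.1: permanent discontinuation | Exempt from the optional rule; persistence not addressed | Conflict |
| Confirmed grade 3 lipase, not or doubtfully related, persistent or recurrent | 5.6.5: interruption, then permanent discontinuation | Exempt through the relatedness exception | Conflict |
| Confirmed symptomatic hyperlactatemia, pH < 7.3, not life-threatening (grade 3 lactate), not or doubtfully related | 5.6.3: stop regimen and withdraw | Exempt through the relatedness exception | Conflict |
| Same syndrome without acidosis (grade 2 lactate value) | 5.6.3: stop regimen and withdraw | No specific criterion | Gap |
| Grade 2 allergic reaction worsening within grade 2 | 5.5.2: stop and withdraw | Specific criterion starts at grade 3 | Gap |
| Asymptomatic grade 3 triglycerides or cholesterol | 5.6.2: may continue | Exempt | Agree |
| Asymptomatic grade 3 pancreatic amylase, no pancreatitis history | 5.6.5: evaluate and follow | Exempt | Agree |

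Notes on the rows:

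1. Every exemption is subject to the immediate-health-risk qualifier. The optional list also has a separate item for serious adverse events, so a case that met seriousness would be open to optional withdrawal rather than exempt. The event section would still direct a stop.
2. A doubtful attribution to ETR is plausible for two of the conflicts. Section 5.6.3 describes lactic acidosis as a complication of N(t)RTI therapy, and 5.6.5 associates pancreatitis mainly with ddI and d4T. The opening of 5.6 adds that ETR may also be a cause.
3. The grade 2 label in the fourth row is the grade of the lactate value alone, assuming no acidosis. The accompanying symptoms have their own grades.
4. Worsening within grade 2 can occur, because Addendum 2 puts both localized urticaria needing medical intervention and mild angioedema not needing it at that grade. Once the reaction reaches grade 3, both sections withdraw the subject.
5. Sections 5.6.1 and 5.6.5 direct discontinuation of medication and do not mention withdrawal from the trial. Sections 5.5.2 and 5.6.3 mention both. The comparison still holds, because by its title 5.2.5 covers removal from therapy as well as from assessment.

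**The case against.** The strongest reply is that the event sections are refinements that sites are told to use. Section 5.4.3.1 sends them to 5.5 and 5.6 and names allergic reaction, hyperglycemia and lactic acidosis. Section 5.6.1 repeats the position that asymptomatic grade 3 glucose may continue, then adds a narrower case: persistence despite treatment. The exemptions in 5.2.5 qualify an optional rule and do not forbid a stop. The openings of 5.5 and 5.6 leave management to the investigator, and the wording is *should*. The investigator-safety item allows withdrawal in any of these cases.

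Much of this stands. The event-section wording is direction under investigator discretion, not an absolute order. A general rule with later escalation is a fair reading of the glucose text. The reply does not remove the problem, however. Section 5.4.3.1 does not name pancreatitis and does not say that 5.5 and 5.6 override 5.2.5. The exemptions do not refer to the escalation cases. The investigator-safety item permits a stop but does not say which text governs.

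A reader might infer that in all five situations 5.2.5 tells the site to keep the subject on ETR. The documents do not support that for the two gaps: 5.2.5 is silent there, does not call its lists exhaustive, and has a general item that can cover both.

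The conflict is also limited in time. Once CRF collection ends, toxicity management under 5.5 and 5.6 passes to local standard of care, and an ongoing subject's next planned visit under Amendment 3 is the last with data collection. A correction now would change little of the analysed data. The 5.2.5 lists carry no such time limit.

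**Conclusion.** The point holds as an inconsistency of text. Direct conflicts affect three event types: persistent asymptomatic grade 3 glucose without pre-existing diabetes, and grade 3 lipase or lactate events judged not or doubtfully related. Two further situations are gaps in 5.2.5, not contradictions. The conclusion assumes that the immediate-health-risk qualifier is not met and, for lipase and lactate, that the investigator attributes the event elsewhere.

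An effect on the discontinuation and disposition tables is possible but cannot be sized. A reader might infer that the counts are distorted, or that these rules governed all CRF data since the trial began in December 2009. Neither follows. No event counts or site practices are given. The earlier protocol text is not supplied, and the Amendment GEN-III summary lists 5.2.5, 5.5 and 5.6 among the sections it changed.

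The correction is still worth making, because the text bears on stopping decisions for individual subjects.

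**What to change.** Reconcile 5.2.5 with 5.5.2, 5.6.1, 5.6.3 and 5.6.5. Cross-reference the event-section triggers in the 5.2.5 lists and exceptions, or bring the event sections into line with 5.2.5. State which section takes precedence when they differ, and extend the pointer in 5.4.3.1 to pancreatitis. Which clinical rule applies is the sponsor's decision, and this review takes no side.

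The cost is protocol wording only, with no new assessments or data. A listing flag showing which section each stop was based on is not proposed: neither document describes such a field, and 5.2.5 asks only for the date and reason of discontinuation on the CRF.
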